2 STUDY OBJECTIVES

The objective of the study is to evaluate the safety and effectiveness of the Imagio for the visualization and classification of suspicious masses when compared to the Imagio ultrasound component. The following outcomes will be evaluated to determine whether Imagio:

- 1. Has superior specificity relative to IUS (primary) with non-inferior sensitivity (secondary) relative to IUS.
- 2. Has clinically acceptable predictive value of a positive test (PPV) and of a negative test (NPV) for a range of possible breast cancer prevalence.
- 3. Downgrades benign masses classified as BI-RADS 3, 4a, or 4b according to IUS.
- 4. Downgrades benign masses classified as BI-RADS 3, 4a or 4b according to the site investigator.
- 5. Upgrades malignant masses classified as BI-RADS 3, 4a, or 4b relative to IUS.
- 6. Achieves a high degree of concordance with the biopsy outcome.
- 7. Is safe.

Color or power Doppler data may be optionally collected during the conventional diagnostic ultrasound examination at the discretion of the site investigator for research purposes. Data from Imagio evaluation of lymph nodes will also be optionally collected for research purposes.

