6.4.1 Statistical Endpoints

The following statistical metrics are to be determined for each image set relative to the histopathology diagnosis:

- 1. True-positive rate or sensitivity (Se)
- 2. Specificity (Sp)
- 3. Concordance (percent true positive [TP] or true negative [TN])
- 4. Positive likelihood ratio (PLR = Se/(1-Sp))
- 5. Negative likelihood ratio (NLR = Sp/(1-Se))
- 6. Predictive values of a negative test (NPV = TN/(FN+TN))
- 7. Predictive values of a positive test (PPV = TP/(FP+TP))
- 8. Odds ratio (OR = (TP/FP)/ (FN/TN)).

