Variable referral patterns across sites are expected. The referral pattern also varies depending on study site (academic vs. private practice), age, risk factors (family history of breast cancer, obesity), and breast BI-RADS density. Note that pre-screening and referral patterns influence diagnostic performance, helping to explain a breast cancer detection rate (BCDR) ranging between 18% and 40%. Endpoints of family history of breast cancer and obesity were not collected in this study.

The histologic findings of the biopsy procedure will serve as a gold standard for Imagio and the decision to not recommend a biopsy during the first 12 months will be regarded as evidence no of disease (True-Negative) for those not recommended for biopsy. Images will be assessed according to if the biopsy was performed immediately, delayed, or irrespective of timing through the 12 month follow-up interval.

High risk histologies will be analyzed separately from benign and malignant histologies in all data analyses. This reflects current practices where high risk masses are considered to be benign histologies but are always removed.

In general, superiority will be assessed using a two-sided 99% lower bound \geq 0 while non-inferiority will be assessed using a one-sided 99.5% lower bound greater than or equal to the non-inferiority margin.

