- The specificity of the test is defined as TN/ (TN + FP)
- The concordance of the test is defined as (TP + TN)/N
- The positive likelihood ratio is defined as TPR/FPR
- The negative likelihood ratio is defined as (1 TPR)/(1 FPR)
- The positive predictive value (PPV) is defined as TP/(TP + FP)
- The negative predictive value (NPV) is defined as TN/ (TN + FN)
- The *odds ratio* (OR) is defined as (TP/FP)/(FN/TN)

Given that biopsy decisions are made using the 2% POM, POM levels >2% have limited relevance to the 2% threshold now widely used for making biopsy decisions.

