8.7.4 Other Secondary Analyses

The sensitivity, specificity, concordance, PPV, NPV, PLR, NLR, and odds ratio for Imagio and the Imagio ultrasound component will be displayed for 2% POM and assessed using 99% confidence bounds.

Additionally, sensitivity and specificity results will be separately displayed for Imagio and the Imagio ultrasound component for the pre-defined subpopulations as descriptive statistics.

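### PPV and NPV are defined only as raw 2x2 ratios, so the planned analysis does not address the objective of judging them over a range of cancer prevalence

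*Protocol*

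**What the plan says.** The objective, in section 2 and again in the synopsis, is to determine whether Imagio "Has clinically acceptable predictive value of a positive test (PPV) and of a negative test (NPV) for a range of possible breast cancer prevalence". The protocol gives no prevalence range for this objective and no limit of acceptability.

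The definitions appear twice:

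- Section 8.5: "The positive predictive value (PPV) is defined as TP/(TP + FP" and "The negative predictive value (NPV) is defined as TN/ (TN + FN" (closing brackets omitted).
- Section 6.4.1: "Predictive values of a positive test (PPV = TP/(FP+TP" and "Predictive values of a negative test (NPV = TN/(FN+TN" (closing brackets omitted).

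The planned analysis is in section 8.7.4, where eight accuracy measures, PPV and NPV among them, "will be displayed for 2% POM and assessed using 99% confidence bounds". Prevalence is not mentioned there. Section 8.5 also builds separate 2x2 tables for immediate biopsies, delayed biopsies, all biopsies, and all cases including those not biopsied.

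The one range of cancer frequency in the protocol is in section 8.1.1, which attributes to referral patterns a "breast cancer detection rate (BCDR) ranging between 18% and 40" percent. It is not connected to PPV or NPV.

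**The concern.** Sensitivity and specificity are each conditional on disease status, so they can be carried to another case mix under an assumption of stability. PPV and NPV taken as raw ratios cannot, because they depend on how many cancers and benign masses fall in the table. This sample is restricted to women with BI-RADS 3, 4 or 5 masses, and section 8.1.1 itself says that referral patterns vary between sites and influence diagnostic performance.

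If the plan is followed as written, the report will show predictive values at whatever cancer fractions the analysed case sets happen to have. It will not say what a positive or negative Imagio result means in a practice with fewer or more cancers, which is the question the objective poses. If the prevalence values and the limit of acceptability are left until the results are known, both can be chosen to suit them.

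**Working it through.** **Plan's own figure.** The protocol states no PPV or NPV, so there is none to reproduce. The planning values used below can be checked against its sample sizes by exact binomial calculation at one-sided 0.005:

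- Table 8: n = 1,160, 40% against 45%, power 80.4%.
- Table 9: n = 360, 90% against 95%, power 80.4%.

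Both agree with the stated 80%.

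**Inputs.**

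- Specificity (Sp) 45%: alternative in Table 8.
- Sensitivity (Se) 95%: alternative in Table 9. Section 8.2.2 expects at least this value.
- Sensitivity 96.5%: implied by Table 7. With 94% positive on both, 5% discordant and no difference, each modality has 94% + 5%/2 = 96.5%.
- Prevalence (p) 18% and 40%: the detection-rate range in section 8.1.1, borrowed for illustration.
- Planning counts: 420 cancers (Table 7) and 1,160 benign masses (Table 8).

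**Step 1: what the raw ratios give.** With Se 95% and Sp 45%, TP = 399, FN = 21, TN = 522 and FP = 638.

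- PPV = 399/(399 + 638) = 38.5%.
- NPV = 522/(522 + 21) = 96.1%.

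This is one pair, valid at a cancer fraction of 420/1,580 = 26.6%.

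**Step 2: the same test at other prevalences.**

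- PPV = Se·p / [Se·p + (1 − Sp)(1 − p)]
- NPV = Sp(1 − p) / [Sp(1 − p) + (1 − Se)p]

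For Se 95%, Sp 45%:

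- p = 18%: PPV = 0.171/(0.171 + 0.451) = 27.5%. NPV = 0.369/(0.369 + 0.009) = 97.6%.
- p = 40%: PPV = 0.380/(0.380 + 0.330) = 53.5%. NPV = 0.270/(0.270 + 0.020) = 93.1%.

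For Se 96.5%, Sp 45%:

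- p = 18%: NPV = 0.369/(0.369 + 0.0063) = 98.3%.
- p = 40%: NPV = 0.270/(0.270 + 0.014) = 95.1%.

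**Step 3: reading the results.** From 18% to 40% prevalence, PPV roughly doubles. Cancers per 1,000 test-negative masses rise from 24 to 69 at Se 95%, and from 17 to 49 at Se 96.5%. At the null values of Tables 8 and 9 (Se 90%, Sp 40%), PPV goes from 24.8% to 50.0% and NPV from 94.8% to 85.7%. The single pair in step 1 shows none of this spread.

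**The case against.** The strongest reply has four parts.

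*The conversion is available from planned results.* Section 8.7.4 already estimates sensitivity, specificity and both likelihood ratios with 99% bounds, and these determine PPV and NPV at any prevalence. This stands. A reader might infer that the objective cannot be answered from the trial, and the protocol does not support that. What is missing is the step that answers it.

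*The prevalence grid belongs in the SAP.* The SAP is not at hand, and a grid of values could sit there. But the protocol does not leave the definition open: it fixes raw ratios in two sections. Section 9.12 says the SAP is developed in accordance with the protocol's statistical section, so a SAP that follows it would inherit them. The ratios are standard in themselves. The fault is that they do not match the stated objective.

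*More than one value will be reported.* This is correct. The four tables by biopsy status in section 8.5 each have their own cancer fraction, so it would be wrong to say that the trial yields a single PPV and NPV. Those fractions are observed, not chosen, and sensitivity and specificity may differ between such selected groups along with prevalence.

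*Little depends on it.* PPV and NPV enter none of the six hypotheses and carry no type I error. This limits the weight of the point but does not remove a stated objective.

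It is also tempting to say that extending accrual to reach 1,000 benign masses distorts the cancer fraction. The protocol does this by enrolling more subjects, not by selecting benign cases, so that reading is not supported.

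**Conclusion.** The point holds as a mismatch between a stated objective and the analysis defined for it. It deserves correction but does not affect the primary or secondary hypothesis tests. Over the illustrative 18% to 40% range at specificity 45%, NPV falls by 4.5 percentage points at sensitivity 95% (97.6% to 93.1%) and by 3.2 points at 96.5% (98.3% to 95.1%). PPV at sensitivity 95% rises by 26.0 points.

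These figures assume the protocol's planning values and that sensitivity and specificity stay the same across case mixes. They also borrow a detection-rate range that the protocol does not tie to this objective.

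A reader might infer from the 2% probability-of-malignancy threshold that NPV must reach 98%, and that it fails to do so throughout this range. Neither follows. The 2% threshold is the positivity cut-off for an individual mass, and the protocol sets no 98% criterion for NPV. At the sensitivity implied by Table 7, NPV at 18% prevalence is above 98% in any case.

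**What to change.** In sections 8.5 and 8.7.4 (with a cross-reference from 6.4.1):

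1. Add PPV = Se·p/[Se·p + (1 − Sp)(1 − p)] and NPV = Sp(1 − p)/[Sp(1 − p) + (1 − Se)p], for Imagio and for IUS, over a pre-specified grid of p that includes 18% to 40%, with 99% bounds.
2. State the assumption that sensitivity and specificity carry over across case mix.
3. Keep the raw ratios as descriptive results, each labelled with the observed prevalence of its table.
4. State, before results are seen, what the sponsor regards as acceptable PPV and NPV, and at which prevalences.

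If the bounds are obtained through the likelihood ratios, first reconcile the negative likelihood ratio. Section 6.4.1 gives Sp/(1 − Se), which is 9.0 at Se 95% and Sp 45%. The form in section 8.5, reading it with the minus signs that the text extraction appears to have lost, is the inverse, 0.11.

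The cost is a change of wording and one extra table from estimates already planned. The downside for the sponsor is that NPV will look less favourable at the higher prevalences.

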8.6. Sample Size Calculations

The sample size calculations for the Pivotal Study may be increased based on the n=800 interim analysis results. The Pilot Study results will solely be used to validate the algorithm and will not count towards the Pivotal Study sample size.

The interim analysis will provide key information to check the preliminary assumptions regarding the degree of correlations between Imagio and IUS. Imagio can theoretically succeed with improvements relative to the above two diagnostic gray scale citations (25, 26) with success

optimized if Imagio can rule out suspicious benign cases (minimizing the false-positive percents). The following table summarizes the specificity superiority tests to detect a conservative absolute 6% advantage which can be performed with 90% power for 860 benign masses assuming 20% discordant.

Table 6: 99.5% Superiority: McNemar's test (Specificity Difference: Paired Proportions

	1
Test significance level, $lpha$	0.5%
Expected difference, $\delta = \pi_1 - \pi_2 $	6%
Proportion discordant, $\eta = \pi_{10} + \pi_{01}$	20%
Power (%)	90
n (number of pairs)	860

The following table summarizes the sensitivity non-inferiority margin (5%) which can be ruled out with 90% power for 420 cancer masses.

Table 7: 99.5% Non-inferiority Confidence Bound: Sensitivity Difference: Paired Proportions (simulation)

	1
Confidence level, 1- $lpha$ (one-sided)	99.5%
Expected difference, π_{T} - π_{S} , Δ_{1}	0%
Proportion discordant, $\eta = \pi_{10} + \pi_{01}$	5%
Proportion both yes, π_{11}	94%
Lower limit for π_T - π_S , LL	-5%
Power (%)	90
n (number of pairs)	420

The following table displays the threshold needed to reject the null hypothesis of 40% specificity with 80% power according to a 99.5% lower bound for 1,160 benign masses. An observed 45% specificity would reject the 40% null hypothesis.

Table 8: 99.5% Exact Lower Bound: Specificity

	1
Test significance level, 1- α	99.5%
Null hypothesis proportion,	π_0 40%
Alternative proportion, π_A	45%
Power (%)	80
N	1160

Seno Clinical Study Protocol: PIONEER-01
300176 Rev 8 PIONEER 01 Protocol Amendment 3.2

The following table displays the threshold needed to reject the null hypothesis of 90% sensitivity with 80% power according to a 99.5% lower bound for 360 cancer masses. An observed 95% sensitivity would reject the 90% null hypothesis.

Table 9: 99.5% Exact Lower Bound: Sensitivity

	1
Test significance level, 1- α	99.5%
Null hypothesis proportion, π_0	90%
Alternative proportion, π_A	95%
Power (%)	80
N	360

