The Pilot Study (Pilot Phase of the Pivotal Study) data will be used to validate the existing algorithm to a pre-determined diagnostic rule set based on OA image characteristics established in a previously conducted independent Feasibility Study. The Pilot Study will collect imaging data from 100 subjects passing Quality Assurance review conducted by three central radiologists blinded to clinical history and histopathology outcome. Then a pool of at least 20 other independent radiologists (readers) not affiliated with any sites will be prospectively trained and then tested for proficiency using the image sets constructed by the central radiologists using the last 70 of the 100 Pilot cases. The first 30 cases will be used to familiarize readers with the image sets, the viewing logistics, and the eCRF to be completed, prior to reader proficiency testing. Upon establishing and meeting prospective rules for proficiency (based on Imagio sensitivity [missing at most one cancer] and Imagio specificity ≥30% after excluding the first 30 cases to allow for learning), a subset of 7 proficient readers will be selected for purposes of reading IUS and Imagio OA and 3 other readers will be selected to share the reimbursement reads of multiple combinations of imaging modalities with or without Imagio, The registration readers will be selected at random based on availability and once all readers are tested for proficiency; reimbursement readers will be selected by the Seno Medical Director. All registration readers will be proficiency tested and selected prior to making any Pivotal Study i.e., reads for subjects 101 and beyond, which will constitute the Pivotal Study. All effectiveness analyses will be conducted at the mass-level; it is projected that no more than 5% of all subjects will have multiple masses. A minimum of 100 Pilot Study masses and at least 1,700 Pivotal Study masses passing QA review and excluding enrollment failures are to be included. Enrollment will continue until there are 100 Pilot Study masses and at least 1,700 Pivotal Study masses that pass both criteria. The 100 Pilot Study cases will be used for education, training, and publication purposes; only the Pivotal Study cases will be used to support Imagio registration for this indication for use. All selected registration readers will evaluate all masses according to a MRMC design. To mimic the real world setting as closely as possible, all readers will receive feedback on the histopathology results in read only mode following their case reads after completing their locked evaluations; readers may not change results after receiving feedback. For the Pivotal Study, subsets of 5% of registration image sets and 2.5% of all reimbursement image sets will be reread to assess learning and consistency; the first reads will be used in the data analyses for registration and reimbursement. The PMA filing will be based

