8. STATISTICAL METHODS

8.1 General Considerations

8.1.1 Statistical Strategy

This is a MRMC design involving two image sets (Imagio and its' ultrasound component) for registration (according to 7 independent readers) and multiple combinations of image sets for reimbursement (according to 3 other independent readers). The registration readers will review all cases while the reimbursement readers will read multiple combinations of image sets. The PMA filing will be based on the registration results with the reimbursement results to be submitted at a later date.

A total of at least 1700 women at 16 US sites are planned to undergo an Imagio evaluation following prospective enrollment, provided there are a sufficient number of benign masses (at least 1,000 masses) and, if there is not a sufficient number, then the total number of subjects will increase to achieve at least 1,000 benign masses. Subjects with an undiagnosed suspicious finding within the previous 45 business days, by palpation or by a screening or diagnostic methodology other than ultrasound, and scheduled to undergo a conventional diagnostic ultrasound will be prospectively screened. Subjects with only a BI-RADS 1 or BI-RADS 2 classification will be regarded as screen failures. This strategy reduces referral bias and accounts for a consecutive series of BI-RADS 3 and BI RADS 4 cases not discovered according to CDU. Once a decision has been made to biopsy (yes or no), the subject will then undergo an Imagio evaluation of all masses to be biopsied (up to a total of three per subject from both breasts). The Imagio results will not be used to decide whether or where to biopsy or to reverse the decision to biopsy; also no study-related follow-up is planned after the biopsy.

The analyses will be performed at the mass level since some subjects will have more than one mass biopsied. It is expected that no more than 5% of all subjects will have multiple masses so no repeated measures analyses are planned, that is, all lesions will be treated as independent observations.

Subjects will be drawn from the following four subpopulations selected by the site investigator to undergo diagnostic ultrasound and then Imagio:

- Callbacks for additional evaluation of suspicious area(s) identified by imaging other than ultrasound.

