A total of 7 independent radiologists will be assigned per each case to independently evaluate both image sets (IUS and Imagio) per subject. In addition, 3 other independent readers will perform the reimbursement reads. All independent readers will evaluate all Pivotal Study cases; the readers will also review 5% of all cases to assess temporal trends and consistency; the initial evaluation will be used in all analyses.

Each registration reader will review the data from the two image sets (IUS, Imagio) for each case; each reader will evaluate Imagio according to a pre-determined diagnostic rule set based on OA image characteristics and will similarly evaluate IUS according to another pre-determined diagnostic rule set and each reader will estimate the probability that the mass is cancer on a scale from 0% to 100% in 5% increments (1% if \leq 10% or \geq 90%). Readers will assess IUS and Imagio in this pre-defined order during independent review sessions; this pre-defined order is consistent with medical practice.

Registration readers will also have access to the results of two locked nomograms to separately predict the POM and the probability of cancer. These nomograms were constructed from the Pilot Study cases using a linear model for the POM and a logistic regression model for the probability of cancer. The nomograms are constructed from the five feature scores for Imagio from a blinded review performed by [name]. The registration readers do not need to use the results of the nomograms in making their POM judgments, but they will immediately see the two predictions as soon as they score the five

features. The sensitivity and specificity of the nomograms will also be evaluated using the average predicted score; if the average is ≤ 0.1 , then the case is predicted to be benign.

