8.7. Analyses

8.7.1 Sensitivity and Specificity

The specificity for Imagio relative to the Imagio ultrasound component (IUS) will be assessed using a one-sided 99.5% lower confidence bound. The goal is to establish at least a 6% absolute advantage in specificity for Imagio vs IUS.

Seno Clinical Study Protocol: PIONEER-01
300176 Rev 8 PIONEER 01 Protocol Amendment 3.2

The sensitivities and specificities will be displayed for Imagio relative to IUS; in these displays, the consequences of Imagio (positive vs. negative) will be considered and compared using a generalized linear model (GENMOD) to account for correlated outcomes among the readers.. Additional analyses will be performed using the nomograms for the POM and the diagnosis based on the five Imagio features. The first nomogram models the probability of malignancy (NPP) while the second nomogram models the probability of cancer (NPC). The sensitivity and specificity of the averaged prediction (NPP and NPC) being ≥ 0.1 or ≤ 0.1 will be evaluated. The ability of the nomogram to downgrade benign masses with IUS POM $\leq 30\%$ and CDU POM $\leq 30\%$ will also be assessed. The linear regression (NPP) and the logistic regression (NPC) models behind the predictions are based solely upon the Pilot Study data.

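### Section 8.1.1 analyses all lesions as independent although one subject can supply up to three; the H1 and H2 bounds should cluster by subject

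*Protocol*

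**What the plan says.** Section 8.1.1 sets the analysis at mass level and states that "no repeated measures analyses are planned, that is, all lesions will be treated as independent observations". The reason given is that few subjects will have several masses; the synopsis says the same: "it is projected that no more than 5% of all subjects will have multiple masses". The same section has Imagio performed on all masses to be biopsied, "up to a total of three per subject from both breasts". The Biopsied Group criteria in section 6.2.2 require a biopsy of each suspicious mass. For unbiopsied subjects with several masses, that section has only one mass followed.

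On readers, section 8.1.1 says: "A total of 7 independent radiologists will be assigned per each case to independently evaluate both image sets". Section 8.7.1 has the two image sets "compared using a generalized linear model (GENMOD) to account for correlated outcomes among the readers". The correlation named there is between readers, not between masses of one woman.

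Section 8.6 gives the power for H1 (Table 6): "which can be performed with 90% power for 860 benign masses assuming 20% discordant". For H2 (Table 7) it gives a 5% margin "which can be ruled out with 90% power for 420 cancer masses". Section 8.1.1 also sets a floor on the benign masses: "the total number of subjects will increase to achieve at least 1,000 benign masses".

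**The concern.** A low share of multi-mass subjects makes within-subject correlation unimportant in size, but it does not make the masses independent. Where the Imagio-minus-IUS difference tends to go the same way for two benign masses, or two cancers, of one woman, an analysis that ignores the subject counts more information than it has. The error favours the device: the 99.5% bounds for the two registration comparisons come out a little too narrow and the true one-sided error a little above 0.5%. The rule is written into the protocol, and section 9.12 has the statistical analysis plan developed in line with the protocol's statistical section, so the plan would inherit it.

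**Working it through.** **The protocol's own figure.** Inputs from Table 6: difference δ = 0.06, discordant proportion η = 0.20, level 0.5% (it reproduces as one-sided), power 90%.

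- n = (z₀.₉₉₅√η + z₀.₉₀√(η − δ²))² / δ² = (2.576 × 0.4472 + 1.282 × 0.4432)² / 0.0036 = 822.
- With continuity correction, (n/4)(1 + √(1 + 4/(nδ)))² = 855.
- Exact McNemar power is 0.908 at 860 masses and 0.950 at 1,000.

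Table 6 is therefore sound as a calculation with one pair of reads per mass and independent masses. For Table 7 (both positive 94%, discordant 5%, expected difference 0), simulated power at 420 masses is about 0.94 with a score bound and 0.97 with a Wald bound. A Newcombe bound without the correlation term gives 0.892.

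**Effect of ignoring the subject.** The design effect is DEFF = 1 + ICC × (Σm²/Σm − 1), where m is the number of masses per subject. Take 100 subjects, 5 of them with several masses:

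- two each: Σm = 95 + 10 = 105, Σm² = 95 + 20 = 115, so Σm²/Σm − 1 = 0.0952;
- three each: Σm = 95 + 15 = 110, Σm² = 95 + 45 = 140, so Σm²/Σm − 1 = 0.2727.

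The ICC is that of the paired difference. The protocol gives no value, so 0.02 to 0.5 is an assumption. A nominal 2.576 bound has true one-sided error P(Z > 2.576/√DEFF).

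| ICC | Masses each | DEFF | True SE / assumed SE | One-sided alpha |
|---|---|---|---|---|
| 0.02 | 2 | 1.002 | 1.001 | 0.50% |
| 0.05 | 2 | 1.005 | 1.002 | 0.51% |
| 0.2 | 2 | 1.019 | 1.009 | 0.54% |
| 0.5 | 2 | 1.048 | 1.024 | 0.59% |
| 0.02 | 3 | 1.005 | 1.003 | 0.51% |
| 0.05 | 3 | 1.014 | 1.007 | 0.53% |
| 0.2 | 3 | 1.055 | 1.027 | 0.61% |
| 0.5 | 3 | 1.136 | 1.066 | 0.78% |

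The table takes the 5% share to hold within the truth class analysed and puts every mass of a multi-mass subject in that class. Specificity uses benign masses only and sensitivity cancers only. A subject with one of each therefore adds no clustering to either.

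A simulation at ICC 0.2 to 0.5 (40,000 trials, about 1,000 masses) agrees in size. The bound that ignores subjects rejects in 0.60–0.65% of trials (two each) or 0.65–0.79% (three each). With clustering by subject the figure is 0.52–0.57%.

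**Effect on information.** At ICC 0.5 the required 1,000 benign masses count as 1,000/1.048 = 955 or 1,000/1.136 = 880. Both exceed 860, and exact one-read power is 0.939 and 0.916.

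**Why Tables 6 and 7 are lower bounds for fixed readers.** If each of seven fixed readers has the assumed gain and discordance, the averaged difference has variance V = (v/n)(1 + 6ρ)/7, with v = 0.20 − 0.06² = 0.1964 and ρ the between-reader correlation. The factor (1 + 6ρ)/7 cannot exceed 1. Power at 860 is P(Z > 2.576 − 0.06/√V): 0.918 at ρ = 1 and 0.990 at ρ = 0.6. For H2 at 420, with v = 0.05 and margin 0.05, it is 0.978 at ρ = 1.

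**The case against.** The best defence is that the assumption is disclosed, justified on the spot by the 5% projection, and further limited because unbiopsied subjects contribute one followed mass. The size also depends on an ICC with no source. In a paired design, a subject effect common to both image sets largely cancels. In an illustrative simulation, a single-modality ICC of 0.11–0.46 left an ICC of only about 0–0.02 in the difference. At 0.02 to 0.05 with two masses each, alpha is 0.504–0.509%. All this stands. It is why the narrowing is stated conditionally and why the upper end of the table should not be read as an estimate. It does not justify keeping the rule, because the analysis can allow for the correlation without knowing its size.

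A reader might go further and infer that the 90% in section 8.6 is wrong, or the study underpowered, because seven readers are planned and Tables 6 and 7 contain no reader term. The documents do not support that. The tables are labelled as paired proportions with n as the number of pairs, Table 6 reproduces on that basis, and for fixed readers more reads cannot lower the power. For inference to readers in general, power would depend on a reader-by-modality SD that the protocol does not give. Section 8.7.1 does not define such inference for H1 or H2, so nothing is claimed about it here.

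**Conclusion.** The concern holds as a minor point about one sentence in section 8.1.1. If differences of same-class masses are positively correlated within a subject, the H1 and H2 bounds are slightly too narrow: one-sided alpha is about 0.50–0.59% with two masses per multi-mass subject and 0.51–0.78% with three, against a nominal 0.5%.

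This rests on the assumed ICC range of 0.02 to 0.5 and on the 5% projection holding within each truth class. Given those, the figures are upper bounds, since every mass of a multi-mass subject is placed in one class. The protocol states the 5% for all subjects, not by class; if multi-mass subjects were concentrated in one class, the effect there would be larger. Material inflation of the error rate is not shown, and neither is a shortfall in power or an arithmetic error in Tables 6 or 7.

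**What to change.** In section 8.1.1, delete the independence sentence and state that the GENMOD analyses of H1 and H2 use subject as the cluster. Subject is the higher level and contains all seven readers' reads of all her masses, so one identifier covers both sources of correlation. The cost is a line of text, a changed cluster identifier in the program and marginally wider bounds. No subjects, masses or readers are added. The gain is also modest: in the simulation with two masses each, the error rate falls by about 0.1 percentage point or less.

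Optionally, add a note to Tables 6 and 7 that they assume one read per modality on each mass and give lower bounds on power for seven fixed readers who each show the assumed difference and discordance. This clarifies the tables and corrects no error.
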